#### 6.3.3 Coefficient of Variation (CV)

CV will be defined as  $(100 * \text{MSE}) / \text{Mean tHb value}$  where MSE = variance of measured values to the line of identity.

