### **1.1 Background and Rationale**

Hemoglobin (Hb) is a protein contained in the red blood cells that is responsible for carrying oxygen from the lungs to tissues throughout the body. The concentration of hemoglobin in whole blood is expressed in grams per deciliter (g/dL). Normal Hb range for adult males is 13 to 18 g/dL and 12 to 16 g/dL for adult females. Sufficient hemoglobin level must be maintained to ensure adequate tissue oxygenation; a person with low levels of hemoglobin is referred to as anemic. Some common causes of anemia are:

- Nutritional deficiency - iron, vitamin B12 and folate
- Abnormal hemoglobin structure - sickle cell or thalassemia
- Acute loss of blood due to traumatic injury or surgical procedure
- Chronic diseases - cancer, kidney and liver failure

If left untreated, anemia can cause several complications, such as:

- Fatigue
- Heart problems, such as arrhythmia
- Death in the case of acute blood loss

To assess a patient's anemia status, a physician would typically request a complete blood count (CBC) test to evaluate hemoglobin levels. The National Committee for Clinical Standards (NCCLS) has published an approved gold standard procedure for the manual measurement of hemoglobin using the cyanmethemoglobin method (HiCN). This method breaks down red blood cells to get the hemoglobin into a solution. Then, the free hemoglobin is oxidized to form methemoglobin and combined with cyanide ions, resulting in cyanmethemoglobin. The concentration of hemoglobin is then determined by shining a light through the solution and measuring how much light is absorbed- specifically at a wavelength of 540 nanometers. Manual HiCN has gradually been phased-out of mainstream laboratory use, because it is time and labor intensive and exposes the operator to harmful reagents. Instead, there are automated analyzers based on the same operating principle of HiCN that are more widely used, such as Beckman Coulter and Advia 120, and Sysmex hematology analyzers. However, HiCN still remains that reference method that all automated analyzers are compared against.

[figure not shown]

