#### 4.2 Study Endpoint

Accuracy will be reported as the root mean squared error ( $A_{RMS}$ ) of the SpHb-tHb parameter. Per ISO 80601 Part 2-61, accuracy of existing pulse oximetry instruments will be reported using  $A_{RMS}$  standard calculations which are also applicable to SpHb testing.

$$Bias = \frac{1}{n} \sum_{i=1}^n (SpHb - tHb)$$

$$A_{RMS} = \sqrt{\frac{\sum_{i=1}^n (SpHb - tHb)^2}{n}}$$

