#### 4.5 Number of Subjects

There will be up to 300 subjects enrolled into this study. The anticipated duration of subject participation in this study will be approximately 1-2 hours in the clinic and up to 72 hours from the time subject leaves the clinic, if subject receives an arterial blood draw. The study enrollment period is expected to be approximately 3 months.

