**6.1.5 Intraclass Correlation Coefficient**

Since this protocol will be run in several clinical sites, an evaluation of the Intraclass Correlationiii was performed. Based on the Site to site variation seen in the earlier study, the Between Site variance component was ██████. The Across Site variance was calculated as ██████. The ICC is found by:

$$ICC = \frac{AcrossSiteVariance}{AcrossSiteVariance + BetweenSiteVariance} = ██████$$

This gives a Sample Size Inflation factor of:

$$██████████████████$$

Therefore, this study will use a minimum of ██████████ total subjects. Additional subjects may be required to fill in demographic bins or account for subject drop out of ██████

In order to collect data across multiple subject health conditions, █ sites will be utilized. The number of subjects per site will be determined by patient availability and patient demographics at each site. This will ensure that other study endpoints related to the distribution of observed hemoglobin values are also met.

Final statistical analysis will be performed on a population set who have enrolled and completed the study procedure as defined per the protocol.

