### 6.3 Additional Analyses, as applicable

#### 6.3.1 Bland-Altman bias plot

6.3.1.1 Bland Altman plots will be provided by site, by subject, and for all data combined.

6.3.1.2 A correction for repeated measures on the same subject and multiple subjects at each site will be applied during the analysis.

6.3.1.3 The limits of agreement will be calculated using the corrected variance components.

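### The CV in section 6.3.3 divides a variance rather than its square root by the mean, so it is not a percentage; separately, the ICC labels and formula in section 6.1.5 disagree and need clarifying

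*Combined protocol and SAP*

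**What the plan says.** **CV.** Section 6.3.3 opens with "CV will be defined as" and gives 100 times MSE, divided by the mean tHb value, "where MSE = variance of measured values to the line of identity". Neither the formula nor the definition contains a square root, and nothing in the section is redacted. The section falls under the 6.3 heading "Additional Analyses, as applicable".

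The plan does take the root for its other error measures. Section 4.2 states "Accuracy will be reported as the root mean squared error" and prints the formula with a radical. Section 6.2.1 does the same for ARMS and for Precision.

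**ICC.** Section 6.1.5 says "Based on the Site to site variation seen in the earlier study, the Between Site variance component was" followed by a redacted value. It then gives an across-site variance, also redacted. The printed ICC is the across-site variance divided by the sum of the across-site and between-site variances. No within-site component is named, and the across-site variance is not defined in the visible text. The ICC feeds the sample size inflation factor and the minimum number of subjects, both redacted.

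**The concern.** The CV should be a unit-free percentage, with a standard deviation (here the root mean squared error) over the mean. Dividing a variance by the mean leaves a quantity in g/dL. An analyst who follows 6.3.3 literally would report a figure labelled CV that is too small when the root mean squared error is below 1 g/dL, which flatters the device, and too large when it is above. This is an error of definition, so more data would not remove it.

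The ICC point is different in kind. An ICC for clustering by site has the between-site variance in the numerator. The text links site-to-site variation to the between-site component, but the formula has that component only in the denominator. Because the ICC drives the inflation factor, a reader must be able to tell which component was in the numerator.

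**Working it through.** The plan states no CV value, and the ICC, inflation factor and minimum N are redacted. There is therefore no figure of the plan's own to reproduce, and the check is of the definitions.

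**Inputs.** Hemoglobin is in g/dL (section 1.1). The illustrative means of 12, 13 and 18 g/dL come from the normal limits in section 1.1: "Normal Hb range for adult males is 13 to 18 g/dL and 12 to 16 g/dL for adult females". The root MSE values, written r, are assumptions. So are the number of sites, the equal site sizes and the ICC values used in part (b).

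**(a) CV**

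- As written: 100 × r² / mean. Units: (g/dL)² / (g/dL) = g/dL.
- With the square root: 100 × r / mean. No units.
- Ratio of written to true: r in g/dL, whatever the mean. The two agree only at r = 1.

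| Mean tHb (g/dL) | r (g/dL) | As written | With square root |
|---|---|---|---|
| 12 | 0.5 | 100 × 0.25 / 12 = 2.08 | 4.17% |
| 12 | 0.8 | 100 × 0.64 / 12 = 5.33 | 6.67% |
| 12 | 1.5 | 100 × 2.25 / 12 = 18.75 | 12.50% |
| 13 | 0.5 | 1.92 | 3.85% |
| 13 | 0.8 | 4.92 | 6.15% |
| 13 | 1.5 | 17.31 | 11.54% |
| 18 | 0.5 | 1.39 | 2.78% |
| 18 | 0.8 | 3.56 | 4.44% |
| 18 | 1.5 | 12.50 | 8.33% |

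Unit check, with r = 0.8 and mean 13 g/dL:

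- As written, in g/dL: 100 × 0.64 / 13 = 4.92.
- As written, same data in g/L (r = 8, mean 130): 100 × 64 / 130 = 49.2.
- With the square root: 100 × 0.8 / 13 = 6.15% and 100 × 8 / 130 = 6.15%.

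A tenfold change of scale multiplies the written statistic by ten, so it is not a percentage.

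**(b) ICC**

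Let B be the site-to-site variance, W the within-site variance, and the true ICC = B / (B + W). Three readings of the across-site variance are possible:

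- It means W, and the between-site variance is B. The formula gives W / (W + B) = 1 − ICC. At a true ICC of 0.05 this is 0.950.
- It means the total B + W. The formula gives (B + W) / (2B + W) = 1 / (1 + ICC). At 0.05 this is 0.952.
- It means B, and the between-site variance is really W. The formula gives 0.050, as it should, and the preceding sentence is mislabelled.

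As a plausibility check, take the usual design effect 1 + (m − 1) × ICC, with 3, 5 or 10 equal sites. Section 4.5 gives the cap: "There will be up to 300 subjects enrolled into this study". Then m = 100, 60 or 30, and the initial independent N that fits under the cap is 300 / (1 + (m − 1) × x), where x is the ICC used.

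| True ICC 0.05 | m = 100 | m = 60 | m = 30 |
|---|---|---|---|
| x = 0.05 | 300 / 5.95 = 50.4 | 300 / 3.95 = 75.9 | 300 / 2.45 = 122.4 |
| x = 0.95 | 300 / 95.05 = 3.2 | 300 / 57.05 = 5.3 | 300 / 28.55 = 10.5 |

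Over true ICCs of 0.01 to 0.20, the initial N is 14.4 to 232.6 with the true ICC and 3.0 to 12.4 with 1 − ICC. An initial N of 3 to 12 is hardly credible as the outcome of a Deming regression simulation. A labelling slip over a correct calculation is the likelier explanation.

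**The case against.** **Limited effect.** The CV is an additional analysis. No visible acceptance limit, hypothesis or decision rests on it, and ARMS will be reported alongside, so a reader could recalculate it. This stands and limits the severity. It does not make the definition right.

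**Lost radical.** A square root sign dropped when the PDF was read would produce the present text, and calling MSE a variance would then be correct. This is possible but weak, because the radicals in sections 4.2 and 6.2.1 survived. A glance at the source page would settle it.

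**Illustrative sizes.** Every root MSE is assumed. The means are normal limits for individuals, while section 4.4 enrols both healthy and non-healthy subjects, so the study mean could lie below 12 g/dL. This stands for the tabulated values. The ratio of written to true CV does not depend on the mean, so the direction of the error is unaffected.

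**Vertical or perpendicular distance.** Section 6.3.3 does not say how distance from the line of identity is measured. Perpendicular distance would make MSE equal to ARMS² / 2. The vertical reading matches the SpHb − tHb error used throughout the plan. On either reading the written statistic is in g/dL.

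**Redaction of the ICC.** The values and the words that might define the across-site variance are blacked out, one of the three readings makes the formula correct, and the phrase about site-to-site variation may introduce the whole variance analysis rather than one component. The cap check also rests on assumed sites and ICCs, and uses the cap because the minimum N is redacted. All of this stands, so the ICC point is a query and not a demonstrated error.

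**Conclusion.** The CV definition is wrong as written and should be fixed. The written value equals the true CV multiplied by root MSE in g/dL: half the true value at 0.5, four fifths at 0.8 and one and a half times at 1.5. These root MSE values are illustrations; the multiplier itself needs no assumption beyond g/dL as the unit. Confidence is high. The ARMS endpoint, bias and precision are not affected.

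The ICC point is held with less confidence. The visible labels and formula do not fit together under the ordinary meaning of between-site variance, but the documents do not show that the planned sample size is wrong.

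**What to change.** In section 6.3.3, write CV = 100 × √MSE / mean tHb and define MSE as the mean of (SpHb − tHb)². The CV is then 100 × ARMS / mean tHb and reuses a quantity already computed. This costs one line of text and no new data.

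In section 6.1.5, define the across-site variance, print ICC = between-site variance / (between-site + within-site variance), and confirm from the stored calculation which component was in the numerator. This costs one line of text and one check. The inflation factor and minimum N need restating only if the check shows that the wrong component was used.

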### 6.4 Criteria for excluding data from quantitative analysis

[REDACTED]

[REDACTED]

[REDACTED]

[REDACTED]

[REDACTED]

6.4.3 Other reasons, to be fully described in the final test report.

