#### 5.3.5 Blood Analysis

- 5.3.5.1 Blood tube(s) will be identified with a unique barcode [REDACTED] for processing and additional analysis.

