#### 5.3.6 Study Completion

Study completion is defined as when the subject has completed the noninvasive device readings and blood draw(s).

- 5.3.6.1 The sensors will be removed and the skin inspected for signs of redness or irritation.
- 5.3.6.2 Subjects will be offered a snack (e.g. granola bar) and/or beverage (e.g. water, juice).
- 5.3.6.3 Subjects will be allowed to leave after medical personnel determine it is safe to do so. Subjects will be encouraged to remain in the study area until they feel fit to leave.
- 5.3.6.4 Vital signs (including heart rate and blood pressure) will be recorded for subject safety monitoring before subject exits the study.
- 5.3.6.5 Subjects will be given post-care instructions for arterial blood draws.
- 5.3.6.6 Subjects who received an arterial stick will be instructed to contact the principal investigator in the event of any potential adverse event up to 72 hours after being discharged from the clinic. AE(s) will be recorded on the CRF and/or Adverse Event Report Form.

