#### 5.4 **Early Withdrawal of Subjects**

##### 5.4.1 Withdrawal of Individual Subjects

Subjects can withdraw from the study at any time for any reason if they wish to do so without any consequences or loss of benefits to which they are otherwise entitled. Subjects may also be withdrawn from the study at any time prior to expected

completion at the discretion of the Principal Investigator or research medical staff for safety concerns, failure to adhere to protocol requirements, malfunction that prevents accurate collection of data, sampling errors, inability to collect noninvasive device and/or hemoglobin readings, administrative reasons, etc.

Any data collected until the time of subject withdrawal may be included in the final data analysis. Information on the subject's withdrawal should either be documented in the medical record or on the CRF and should include clear documentation of the reason for withdrawal to the Sponsor.

No follow-up is required for subjects who did not receive an arterial stick and are withdrawn from the study, as there are no long term effects anticipated from participating in this study. Subjects who received an arterial stick will be instructed on wound care and to contact the principal investigator in the event of any potential adverse event up to 72 hours after being discharged from the clinic. AE(s) will be recorded on the CRF and Adverse Event Report Form.

Subjects that withdraw from the study may be replaced by another volunteer.

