### **9.4 Data Transfer and Storage**

9.4.1 Training on CRF completion will be provided to study personnel prior to data collection.

9.4.2 Original CRFs will be stored in a secure location at site. Original CRFs will be scanned and sent to sponsor.

9.4.3 Only authorized sponsor personnel will have access to study data, and will move it to a secure and backed-up drive at Masimo.

9.4.4 CRFs will be checked for accuracy and completeness of data. If there are inconsistent or missing data points, a data query list will be generated and submitted to the PI or designee, who shall both follow GDP practices for data correction by striking through the old entry, adding in new entry with initial and date, and resend to Masimo the corrected CRF. Once all queries have been resolved, Masimo engineers are notified that data is ready for analysis. To ensure data integrity, Masimo engineers will only have read access to study data, therefore are unable to unintentionally tamper with the original data files.

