### **9.5 Record Retention**

All study information, including but not limited to study correspondence, study logs, device accountability records, consent forms, subject records, and copies of CRFs should be maintained in the Investigator site files.

Study records shall be retained during the study and for a minimum of two years after date of study closure or date when records are not required to support 510(k) clearance. The Institution's own retention policies and regulations may apply in addition to the minimal requirement.

The Sponsor is responsible for verifying study data, retaining records, analyzing data, and authoring study reports.

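### Section 6.4.3 leaves an open category of data exclusions with no visible requirement that they be decided blind to the SpHb-tHb difference, and 6.1.5 and 5.4.1 disagree on withdrawn subjects' data

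*Combined protocol and SAP*

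**What the plan says.** The endpoint (4.2, 6.2.1) is ARMS, the root mean square of SpHb minus tHb over all n pairs. Several sections bear on which pairs make up n.

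- **6.4.3.** After earlier entries that are redacted in the public copy, the exclusion criteria close with "Other reasons, to be fully described in the final test report".
- **6.1.5.** "Final statistical analysis will be performed on a population set who have enrolled and completed the study procedure as defined per the protocol". Section 5.3.6 defines completion as having finished the noninvasive readings and the blood draw(s).
- **5.4.1.** "Any data collected until the time of subject withdrawal may be included in the final data analysis". No criterion says when such data are used. The listed withdrawal reasons include malfunction, sampling errors and inability to obtain readings.
- **6.3.1.2.** For the Bland-Altman analysis, "A correction for repeated measures on the same subject and multiple subjects at each site will be applied during the analysis". More than one pair per subject is therefore foreseen.
- **6.5.** A mixed-effects analysis will assess how missing data affect the accuracy endpoint.
- **9.4.4.** "Masimo engineers will only have read access to study data, therefore are unable to unintentionally tamper with the original data files".
- **9.5.** "The Sponsor is responsible for verifying study data, retaining records, analyzing data, and authoring study reports".

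**The concern.** An open category of exclusions is harmless if the decision cannot be influenced by the result. Here the only visible condition is a description after the fact. The party that analyses the data also writes the report, and no visible text separates the decision from knowledge of the paired difference. Because ARMS squares each difference, it responds most to the pairs most likely to look suspect on inspection. If exclusion tracks the size of the error even in part, and in good faith, reported ARMS is too low.

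The mismatch between 6.1.5 and 5.4.1 is a smaller matter of the same kind. A subject who gives one usable pair and then withdraws before finishing is outside the analysis under one section and optionally inside it under the other.

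**Working it through.** **Do the visible safeguards settle the analysis set?**

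- The duty in 6.4.3 to describe reasons gives disclosure, not pre-specification.
- Read-only access and query resolution (9.4.4) protect the data files. They do not govern which pairs are used.
- The mixed-effects check in 6.5 is the nearest visible sensitivity analysis. It assesses the impact of missing data but does not say which pairs enter ARMS, or that ARMS will be shown with 6.4.3 exclusions restored.
- Documented withdrawal reasons (5.4.1) explain why a subject left, not whether that subject's pairs count.

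**How far could selective exclusion move ARMS?** The plan gives no figure to reproduce: the sample-size inputs and results are redacted and no ARMS limit is visible. What follows is an illustration.

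*Assumptions:* normal differences, zero bias, and a fraction p of pairs removed. The case of 300 pairs is the enrolment ceiling in 4.5 with one pair per subject. The true number of pairs is not visible.

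*All removals are the largest errors.* With z the standard normal quantile at 1 - p/2 and φ the normal density, the ratio of ARMS after removal to ARMS before is √[1 - 2zφ(z)/(1 - p)].

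- p = 2%: z = 2.326, φ = 0.02665; 2 × 2.326 × 0.02665/0.98 = 0.1265; √0.8735 = 0.935, a fall of 6.5%.
- p = 5%: z = 1.960, φ = 0.05845; 2 × 1.960 × 0.05845/0.95 = 0.2412; √0.7588 = 0.871, a fall of 13%.

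*Half are the largest errors, half random.* The random half leaves the expected mean square unchanged, so p/2 replaces p. The ratios are 0.962 and 0.923, falls of 3.8% and 7.7%.

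*Unrelated to error.* No change on average.

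**Against sampling error.** For independent normal pairs with zero bias, the relative SD of ARMS is about 1/√(2n). Simulation gave these mean falls for fully targeted removal:

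| Pairs | SD of ARMS | Fall, 2% removed | Fall, 5% removed |
|---|---|---|---|
| 100 | 7.1% | 6.1% | 12.5% |
| 200 | 5.0% | 6.3% | 12.7% |
| 300 | 4.1% | 6.4% | 12.7% |
| 300, clustered | 5.6% | 6.3% | 12.7% |

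The clustered row assumes 5 sites × 30 subjects × 2 readings, with 50% of the variance between subjects within site and 10% between sites. Fully targeted removal of 2% exceeds one SD in three of the four rows and stays within 1.96 SD in all four. Half-targeted removal of 2% is below one SD in all four.

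**Dependence on n.** For a fixed fraction, the fall is nearly constant across the independent rows. For a fixed number of exclusions it shrinks: dropping the 3 worst pairs costs about 8.5% at n = 100 (3% of pairs) and 3.7% at n = 300 (1%) by simulation, or 8.9% and 3.8% by the formula.

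**Other assumptions.** A bias of 0.5 SD changes little (6.2% and 12.4% at n = 300). Heavier tails enlarge the effect: with t errors on 5 df and 300 pairs, the ratios are 0.875 (2%) and 0.792 (5%).

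**The case against.** The case on the other side has five parts.

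1. *Redaction.* The opening of Section 6 and most of 6.4 are blacked out. A hidden lead-in could say who decides exclusions and when, and could govern 6.4.3 too. This stands. A reader might infer that the plan permits unblinded exclusion, or that 6.4.3 is open whatever the redacted text says. The documents support neither. They show only that no visible text requires blinding. The redacted entries may be specific and objective, and they are not missing from the plan.
2. *Scope.* A reader might infer that the whole set of pairs is discretionary. Discretion is visible only in the catch-all and for withdrawn subjects.
3. *Existing safeguards.* Exclusions must be fully described, withdrawal reasons documented, and the impact of missing data assessed under 6.5. These make exclusions visible to a reader of the report. They do not fix the analysis set beforehand.
4. *Small affected group.* The clinic session lasts about 1-2 hours (4.5), and a subject with all readings and draws is a completer by definition. Only someone who leaves between repeat readings or draws falls between 6.1.5 and 5.4.1. This stands, and is why that point is secondary.
5. *Size.* The 2% and 5% rates and the degree of targeting are assumptions. A reader might infer that a few exclusions generally outweigh sampling error, that more pairs never dilute the effect, or that the study conclusion could change. The first is not general, the second holds only for a fixed fraction, and the third cannot be shown without a visible acceptance limit.

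**Conclusion.** The point holds in limited form. On the visible text, 6.4.3 permits exclusions for unspecified reasons, described only afterwards, with no visible requirement that they be decided without sight of the paired difference. Neither 6.5 nor the duty to describe settles which pairs enter ARMS. The conflict between 6.1.5 and 5.4.1 is real but probably touches few subjects.

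Under normal errors with zero bias, the size runs from zero to the fully targeted bounds worked out above. These are not predictions, and heavier tails would raise them. The change should be made because it is cheap and protects the main accuracy figure. Confidence is medium, because redacted text may already deal with 6.4.3; the disagreement between 6.1.5 and 5.4.1 is visible as it stands.

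**What to change.** 1. Replace the analysis-population sentence in 6.1.5 and the optional wording in 5.4.1 with one rule. ARMS uses all SpHb-tHb pairs from eligible enrolled subjects, including pairs obtained before withdrawal, except those excluded under the pre-specified 6.4 criteria or under 6.4.3 as in step 2.
2. Decide, log and sign any 6.4.3 exclusion before SpHb is linked to the reference laboratory tHb, or have it decided by someone without sight of the paired difference. Section 5.3.5.1 says "Blood tube(s) will be identified with a unique barcode", which may help in holding the link back. That item is partly redacted and who holds the link is not visible, so the second route may be simpler. If redacted text already imposes such a rule, confirm that it covers 6.4.3.
3. Report ARMS with and without the 6.4.3 exclusions. In the version that restores them, keep out only pairs whose reference sample is documented as invalid on grounds that do not depend on SpHb.

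The cost is revised wording, a signed log, one extra ARMS line and possibly a slightly less favourable ARMS. No subjects or procedures are added, and genuinely bad samples can still be removed.
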